4.2 Effectiveness Hypotheses

Primary Effectiveness

No inferences are to be made on the primary effectiveness endpoint; therefore, no hypotheses are formulated.

4.3 Statistical Methods for Effectiveness Analyses

Primary Effectiveness

At Week 1, descriptive statistics will be provided as number of observations, mean, SD, median, minimum, and maximum, along with a two-sided 95% confidence interval.

Similarly, for Dispense and Week 2.

4.4 Multiplicity Strategy

No multiplicity adjustment needs to be considered for the effectiveness endpoints since no formal hypothesis testing will be conducted.

4.6 Interim Analysis for Effectiveness

No interim analysis is planned for effectiveness endpoints.

5 SAFETY ANALYSIS STRATEGY

The focus of the safety analysis will be a comprehensive descriptive assessment of occurrence of adverse events as well as the other listed parameters. Therefore, no inferential testing will be done for the safety analysis.

5.1 Safety Endpoints

The safety endpoints are:

- Adverse events (AE)
- Biomicroscopy Findings
 - Limbal hyperemia
 - Bulbar hyperemia

- Corneal staining
- Conjunctival staining
- Palpebral conjunctival observations
- Corneal epithelial edema
- Corneal stromal edema
- Corneal vascularization
- Conjunctival compression/indention
- Chemosis
- Corneal infiltrates
- Other findings
- Device deficiencies

5.2 Safety Hypotheses

There are no formal safety hypotheses in this study. The focus of the safety analysis will be a comprehensive descriptive assessment of safety endpoints listed in Section 5.1.

5.3 Statistical Methods for Safety Analyses

The analysis set for all safety analyses is defined in Section 2.1. Baseline will be defined as the last measurement prior to exposure to study lenses. For biomicroscopy data, baseline will be defined as Visit 2 for Period 1 and Visit 5 for Period 2. Safety variables will be summarized descriptively.

5.3.1 Adverse Events

The applicable definition of an AE is in the study protocol. All AEs occurring from when a subject signs informed consent to the time of their study exit will be accounted for in the reporting.

Presentation of AEs will be separated into pretreatment AEs, between-treatment AEs, and treatment-emergent AEs as defined below:

- Pretreatment: an event that occurs after signing informed consent but prior to exposure to study lenses
- Between-treatment: an event that occurs one day after last exposure to Period 1 study lenses but prior to exposure to Period 2 study lenses
- Treatment-emergent: an event that occurs from exposure to Period 1 study lenses until subject exits from the study, excluding those classified as between-treatment

The following tables and supportive listings will be provided:

- Incidence of All Ocular Treatment-Emergent Adverse Events
- Incidence of Ocular Serious Treatment-Emergent Adverse Events
- Incidence of Ocular Significant Nonserious Treatment-Emergent Adverse Events
- Incidence of All Nonocular Treatment-Emergent Adverse Events
- Incidence of All Nonocular Serious Treatment-Emergent Adverse Events
- Listing of All Ocular Treatment-Emergent Adverse Events
- Listing of All Nonocular Treatment-Emergent Adverse Events
- Listing of All Ocular Pre-Treatment Adverse Events
- Listing of All Nonocular Pre-Treatment Adverse Events
- Listing of All Ocular Between-Treatment Adverse Events
- Listing of All Nonocular Between-Treatment Adverse Events

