There may also be unknown risks to use of LID233309. Any risk to subjects in this clinical study will be minimized by compliance with the eligibility criteria and study procedures, clinical oversight, and monitoring. Site personnel will educate subjects on proper hygiene and lens handling, and compliance with the use of contact lenses for daily wear according to the protocol. Subjects should be instructed not to wear contact lenses while swimming due to increased risk of infection or while sleeping. Site personnel should advise the subjects to remove contact lenses and return for prompt follow-up of symptoms such as ocular discomfort, foreign body sensation, excessive tearing, vision changes, or hyperemia.

Refer to the IB for additional information.

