7 INVESTIGATIONAL PLAN

7.1 Study Design

[figure not shown]
This is a prospective, randomized, bilateral, crossover, double-masked (study lenses), dispensing, multicenter study comparing the LID233309 lenses and Oasys MF contact lenses.

Subjects will be randomized [REDACTED] and exposed to both test and comparator lenses for bilateral wear. Subjects will be expected to attend 7 office visits and will be dispensed study lenses (test and comparator lenses) for a 14-day duration of bilateral wear each (total of approximately 28 days of lens wear). Between Visits 1 and 2, a washout period (wearing spectacles) of 2 [at least 48 hours] - 4 days after the end of Visit 1 will be required, and between Visits 4 and 5, a washout period (wearing spectacles) of 2 [at least 48 hours] - 4 days after the end of Visit 4 will be required. Subjects will be expected to wear their study contact lenses for at least 10 hours per day, over a 14-day period per study lens. Subjects will be asked to wear study lenses for 16 hours on the days prior to each Follow-up Visit (Visit 3, 4, 6 & 7).

In this trial, as both test and comparator lenses have manufacture specific fitting guides, the PI may become aware of the identity of the lens during fitting. However, the PI must remain masked to the complete randomized sequence which includes study lenses. The investigator will be masked to the dispensed study lenses. The subjects will be masked to both fitting and dispensed study lenses. An unmasked site coordinator will prepare the lenses for both lens fitting and dispensing.

All study contact lenses will be prescribed according to the subject's prescription. CLEAR CARE Cleaning & Disinfecting Solution will be provided for use during the duration of the study.

Figure 7-1 Study Design

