10.5.2 Discontinuations

Discontinued subjects are individuals who voluntarily withdraw or are withdrawn from the study by the investigator after signing informed consent and after randomization.

Subject numbers of discontinued subjects must not be re-used (i.e., subject replacement is not allowed).

Subjects may discontinue from study or study treatment at any time for any reason. Subjects may also be discontinued from study treatment at any time if, in the opinion of the investigator, continued treatment poses a risk to their health.

If a subject discontinues from study treatment, every effort must be made to keep the subject in the study and to continue with the study assessments as specified in the schedule of study procedures and assessments until the final visit.

For subjects discontinuing from the study, the investigator must complete all Exit procedures according to Table 3-1 Schedule of Study Procedures and Assessments and Section 10.5.3, if the subject is willing and able, and if in the opinion of the investigator it is safe for the subject to do so.

The investigator must document the reason for study or treatment discontinuation in the subject's case history source documents.

To ensure the safety of all subjects who discontinue early, investigators must assess each subject and, if necessary, advise them of any therapies and/or medical procedures that may be needed to maintain their health.

10.5.3 Schedule of Procedures and Assessments for Subjects Discontinued from Investigational Product

Other than screen failures, if a subject discontinues from the study, the subject should undergo an Early Exit Visit, as possible. Refer to [Table 3-1](#) and the MOP for details.

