12.6 Safety Analyses

The safety endpoints are:

- AEs
- Biomicroscopy findings
- Device deficiencies

There are no safety hypotheses planned in this study. The focus of the safety analysis will be a comprehensive descriptive assessment of occurrence of AEs as well as the other listed parameters.

All AEs occurring from the time a subject signs informed consent to study exit will be accounted for in the reporting. Safety analyses will be conducted using the safety analysis set on a treatment-emergent basis. Descriptive summaries (frequencies and percentages) for ocular and nonocular AEs will be presented by Medical Dictionary for Regulatory Activities Preferred Terms. AEs leading to study discontinuation, significant nonserious AEs, and SAEs will be identified. Individual subject listings will be provided, as necessary.

Separate individual subject listings will be provided for AEs that occur after signing informed consent but prior to exposure to study lenses, and for AEs that occur during the washout periods.

Each biomicroscopy parameter will be tabulated by its grade. For each biomicroscopy parameter, counts and percentages of eyes that experience an increase of ≥ 2 grades from baseline (last assessment prior to study lens) to any subsequent visit within the same period will be presented. A supportive listing will be generated which will include all biomicroscopy data from all visits within the same period for those eyes experiencing the increase.

Two listings (prior to exposure to study lenses and treatment-emergent) of device deficiencies will be provided. Additionally, each device deficiency category will be tabulated.

No inferential testing will be conducted for the safety analyses.

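### SAP 5.3.1 starts the between-treatment class at last Lens 1 wear, not at the Visit 4–5 washout, so some Period 1 follow-up AEs are only listed while like events after stopping Lens 2 are tabulated

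*SAP*

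**What the plan says.** SAP 5.3.1 sorts AEs into three classes. Pretreatment events precede any study lens exposure. The second class is worded as follows: "Between-treatment: an event that occurs one day after last exposure to Period 1 study lenses but prior to exposure to Period 2 study lenses".

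The third class takes what remains, and its wording sets no limit after the last wear of Lens 2: "Treatment-emergent: an event that occurs from exposure to Period 1 study lenses until subject exits from the study, excluding those classified as between-treatment".

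All five AE incidence tables in that section are restricted to treatment-emergent events. Between-treatment events appear only in listings, for example "Listing of All Ocular Between-Treatment Adverse Events" and its nonocular counterpart.

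Protocol 12.6 plans separate listings for events before exposure "and for AEs that occur during the washout periods". Protocol 7.1 places the later washout as follows: "between Visits 4 and 5, a washout period (wearing spectacles) of 2 [at least 48 hours] - 4 days after the end of Visit 4".

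Protocol 10.5.2 foresees follow-up without wear: "If a subject discontinues from study treatment, every effort must be made to keep the subject in the study", with the scheduled assessments continuing to the final visit.

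**The concern.** The protocol's boundary is a scheduled interval after Visit 4. The SAP's boundary is the subject's own last day of Lens 1 wear, whenever that falls, and it mentions neither Visit 4 nor the washout. If a subject stops Lens 1 early and remains under observation, the SAP class opens inside Period 1 and takes in days that the protocol does not treat as washout.

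Period 2 has no matching cut. Treatment-emergent runs to study exit, so events after stopping Lens 2 remain in the tables. Whether an event in an early stopper is counted can therefore depend on the period in which it arose, and neither document gives a reason for the difference.

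What is at stake is the completeness of the descriptive incidence tables, above all those for serious and significant nonserious ocular events, where one or two events can be the whole result.

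**Working it through.** The plan states no figure on this point, so the check applies the definitions to the visit calendar.

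**Inputs**
- Visit 2 (dispense) is Day 1.
- Visits 3 and 4 each follow the previous visit by 7 −0/+1 days (Protocol Table 3–1, SAP Table 1-1), so Visit 4 falls on Day 15 to 17.
- Visit 5 is 2 to 4 days after Visit 4, so it falls on Day 17 to 21.
- L is the last day of Lens 1 wear, V4 and V5 are the visit days, and Lens 2 starts at V5.

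**Formulas**
- Days labelled between-treatment by the SAP: V5 − L − 1.
- Of these, days on or before Visit 4: V4 − L.
- Whole washout days between the visits: V5 − V4 − 1.

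**Results for an illustrative stop on Day 5**

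| | V4 = 15, V5 = 17 | V4 = 17, V5 = 21 |
|---|---|---|
| Labelled between-treatment | 17 − 5 − 1 = 11 | 21 − 5 − 1 = 15 |
| On or before Visit 4 | 15 − 5 = 10 | 17 − 5 = 12 |
| Whole washout days | 17 − 15 − 1 = 1 | 21 − 17 − 1 = 3 |

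A later stop moves fewer days. With L = 8, V4 − L is 7 to 9, and with L = 11 it is 4 to 6. For a subject whose last wear is on the day of Visit 4 it is 0, and the two documents agree. In Period 2 the number of days removed is 0 whatever the stopping day.

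**Example courses**

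| Course | SAP 5.3.1 class | In a Protocol 12.6 washout? |
|---|---|---|
| Lens 1 worn to Visit 4, onset Day 10 | Treatment-emergent | No |
| Lens 1 stopped Day 5, onset Day 5, examined Day 8 | Treatment-emergent | No |
| Lens 1 stopped Day 5, new onset Day 8, Lens 2 started Day 18 | Between-treatment, listing only | No |
| Lens 2 started Day 18, stopped Day 22, new onset Day 25 | Treatment-emergent | No |
| Lens 1 stopped Day 5, new onset Day 6, exit, Lens 2 never worn | Not clear | No |

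The third and fourth rows are the same course in different periods and receive different classes. In the last row, the SAP definition ends at an exposure that never takes place.

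**Effect on a table.** With 92 subjects per lens as the denominator (the planned completers, used as an assumption), one reclassified subject changes an incidence by 1/92 = 1.1 percentage points and two by 2/92 = 2.2.

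**The case against.** The strongest reply is that the events of most interest do not move. The SAP classifies an event by when it occurs, and Protocol 11.3 requires a date of occurrence for adverse device effects and serious events. Protocol 5.3 says "Site personnel should advise the subjects to remove contact lenses and return for prompt follow-up of symptoms", and a reader might infer that an infiltrate or staining found at that later visit drops out of the tables. The documents do not support this. An event that began during wear, including the one that led to stopping, stays treatment-emergent even if it is examined days later. Only an event with new onset at least one day after the last wear moves, and for such an event attribution to the lens is weaker. This objection stands and narrows the point.

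Other parts of the reply also stand:

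- A reader might infer that for a subject who leaves in Period 1 the between-treatment class runs to exit. That is one reading. The name of the class and the treatment-emergent wording favour the other. The SAP does not settle it.
- A reader might take the gap between about 96 enrolled and 92 completed (4/96 = 4.2%) as the number affected. It is not. Enrolled means consented, so the gap also covers screen failures, fitting failures and Period 2 exits, and it excludes early stoppers who stay and complete.
- Protocol 10.3 calls for exit procedures when a subject is discontinuing the product, and the heading of 10.5.3 points the same way. Neither document describes a specific route to Lens 2 after Lens 1 is stopped, so the affected group could be empty.
- Biomicroscopy increases are counted by visit within the period, and AEs by onset. A reader might call that a contradiction, but these are two conventions. The biomicroscopy outputs keep such signs visible under Period 1.
- Last exposure is not defined in the visible text, and text near the analysis sets is redacted. If it were derived as the Visit 4 date, the problem would vanish for subjects who reach Visit 4.

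None of this explains why the SAP boundary departs from the protocol's, or why only Period 1 has a cut.

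**Conclusion.** The mismatch is real but narrow. On its stated wording, the SAP moves new-onset AEs between the day after last Lens 1 wear and Visit 4 out of the incidence tables. This applies to a subject who stops Lens 1 early, remains under follow-up and later starts Lens 2. The same event after stopping Lens 2 is counted. For a subject who never wears Lens 2, the class is not clearly stated.

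The result is possible under-counting of Period 1 events in descriptive tables: 10 to 12 days of follow-up per affected subject in the Day 5 example, and about 1.1 points of incidence per reclassified subject. A reader might infer a bias toward one lens. The documents give no ground for that, because each lens is worn in both periods under randomized sequences. Nor are events lost, since they remain in the between-treatment listings.

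The conclusion assumes that last exposure means the actual last day of wear. The number of affected subjects is not given and is probably very small. The point is still worth correcting, because it concerns a stated rule and the correction is cheap.

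**What to change.** In SAP 5.3.1:

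1. Define between-treatment as onset from the day after Visit 4 and before first wear of the Period 2 lens, in line with Protocol 12.6.
2. State that, for subjects who stop Lens 1 early or exit in Period 1, events up to Visit 4 or Early Exit remain treatment-emergent under Lens 1.
3. Say where the class ends for a subject who passes Visit 4 but never wears Lens 2. Study exit is the natural choice.

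Apply the same boundary to the between-treatment device deficiency listing in SAP 5.3.3, which uses the label without defining it.

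An identical post-exposure window in both periods would also restore symmetry, but it would not match the protocol's washout wording.

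The cost is two or three sentences and a small change to the AE classification program, with no new data. The downside is that some events arising after wear has stopped will count under Lens 1, as already happens for Lens 2.

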Further, depending upon the nature of the AE or device deficiency being reported, the study sponsor may request copies of applicable portions of the subject's medical records. The investigator must also report all AEs and device deficiencies that could have led to a SADE according to the requirements of regulatory authorities or IRB/IEC.

Intensity and Causality Assessments

Where appropriate, the investigator must assess the intensity (severity) of the AE based on medical judgment with consideration of any subjective symptom(s), as defined below:

Intensity (Severity)

- | | |
|----------|--|
| Mild | An AE is mild if the subject is aware of but can easily tolerate the sign or symptom. |
| Moderate | An AE is moderate if the sign or symptom results in discomfort significant enough to cause interference with the subject's usual activities. |
| Severe | An AE is severe if the sign or symptom is incapacitating and results in the subject's inability to work or engage in their usual activities. |

For every AE in the study, the investigator must assess the causality (related or not related to the medical device or study procedure). An assessment of causality will also be performed by study sponsor utilizing the same definitions, as shown below:

Causality

- | | |
|-------------|--|
| Related | An AE classified as related may be either definitely related or possibly related where a direct cause and effect relationship with the medical device or study procedure has not been demonstrated, but there is a reasonable possibility that the AE was caused by the medical device or study procedure. |
| Not Related | An AE classified as not related may either be definitely unrelated or simply unlikely to be related (i.e., there are other more likely causes for the AE). |

The study sponsor will assess the AEs and may upgrade the investigator's assessment of seriousness and/or causality. The study sponsor will notify the investigator of any AE that is upgraded from nonserious to serious or from unrelated to related.

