1.2 Study Description

Key components of the study are summarized in Table 1-1.

Table 1-1 **Study Description Summary**

[figure not shown]
	
Target to complete: 92
 
Planned to enroll: ~96

Number of Sites	~8 US
Test Product	Alcon serafilcon A Multifocal contact lenses (serafilcon A; LID233309)
Comparator Product	ACUVUE® OASYS MULTIFOCAL with PUPIL OPTIMIZED DESIGN contact lenses (Oasys MF; senofilcon A)
Planned Duration of Exposure	~28 days total duration (test and comparator): Test Product: 14 days Comparator Product: 14 days
Visits	
Prescreening (optional)
 
Visit 1: Screening/Baseline/Lens Fitting
 
Visit 2: Dispense Lens 1 [2 (at least 48 hours) - 4 days after the end of Visit 1*]
 
Visit 3: Week 1 Follow-up Lens 1 [7 -0/+1 days after Visit 2]
 
Visit 4: Week 2 Follow-up Lens 1 [7 -0/+1 days after Visit 3]
 
Visit 5: Dispense Lens 2 [2 (at least 48 hours) - 4 days after the end of Visit 4*]
 
Visit 6: Week 1 Follow-up Lens 2 [7 -0/+1 days after Visit 5]
 
Visit 7: Week 2 Follow-up Lens 2/Exit [7 -0/+1 days after Visit 6]
 
* Washout period with habitual spectacles only after Visit 1 and after Visit 4

A study design schematic is depicted in Figure 1-1.

Figure 1-1

Study Design

[figure not shown]
Study Design
Prospective, Randomized, Double-masked, Cross-over Dispensing Trial

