2 ANALYSIS SETS

2.1 Safety Analysis Set

Safety analyses will be conducted using the safety analysis set on a treatment-emergent basis. As such, the safety analysis set will include all subjects/eyes exposed to any study lenses evaluated in this study. [REDACTED]

[REDACTED], any adverse event (AE) or device deficiency occurring after informed consent and prior to the initial exposure to the study lenses (test or comparator) under evaluation in this clinical protocol will be listed as pretreatment.

For treatment-emergent safety analyses, subjects/eyes will be categorized under the actual study lenses exposed in the corresponding study lens sequence.

Adverse events occurring from the time of informed consent but prior to first exposure to study lenses will be summarized in subject listings.

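### Does listing washout adverse events separately, with no incidence table, leave a device-related event out of the safety profile of the lens worn in Period 1?

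*SAP*

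**What the plan says.** SAP section 5.3.1 sorts adverse events by time into three classes. Pretreatment events fall after consent and before exposure to study lenses. A between-treatment event is "an event that occurs one day after last exposure to Period 1 study lenses but prior to exposure to Period 2 study lenses". Treatment-emergent events run from first Period 1 exposure "until subject exits from the study, excluding those classified as between-treatment".

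The outputs follow that split. The five incidence tables (all ocular, ocular serious, ocular significant nonserious, all nonocular, nonocular serious) are all treatment-emergent. Between-treatment events have two outputs: the "Listing of All Ocular Between-Treatment Adverse Events" and its nonocular counterpart.

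The visible attribution rule in SAP section 2.1 is worded for treatment-emergent analyses: "subjects/eyes will be categorized under the actual study lenses exposed in the corresponding study lens sequence". Protocol section 12.6 calls for separate subject listings for events before exposure "and for AEs that occur during the washout periods". Under protocol section 11.3 the investigator judges every event as "related or not related to the medical device or study procedure", and the sponsor repeats the judgement: "An assessment of causality will also be performed by study sponsor utilizing the same definitions".

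**The concern.** The safety objective is to describe the safety profile of the study products, and the incidence tables are where a reader looks for it lens by lens. The classification in SAP section 5.3.1 depends on timing alone. An event that starts two days after the last Period 1 wear, and that both investigator and sponsor attribute to the lens, is between-treatment. It enters no incidence table, and the visible attribution rule does not reach it.

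A reader who relies on the tables could then see no event for a lens that had one. Causality is collected for every event, so the information needed to place it would be in the database. At stake is the completeness of the per-lens summary, not a test or an estimate of a difference.

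**Working it through.** The plan gives no adverse event rate, so there is no figure of its own to reproduce on this point. The check has two parts.

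**Passages side by side**

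1. Protocol section 12.6 puts safety summaries on a treatment-emergent basis and assigns washout events to separate listings.
2. SAP section 5.3.1 does exactly this: five treatment-emergent incidence tables, no between-treatment table, two between-treatment listings.
3. SAP section 5.3.3 also gives between-treatment device deficiencies their own listing. The three-way split is a consistent convention, not an oversight in one output.
4. SAP section 3 provides a listing of lens sequence assignment. With it, the Period 1 lens of any listed event can be identified.
5. The between-treatment window opens one day after last exposure. An event later on the Visit 4 day, after lens removal, stays treatment-emergent and is tabulated.
6. Biomicroscopy is scheduled at Visits 4 and 5, and SAP section 5.3.2 tabulates findings by visit. Signs present at the end of Period 1 should be found at Visit 4. Signs still present at Visit 5 appear in the by-visit table, although SAP section 5.3 makes that visit the Period 2 baseline.

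**Size of the window for completers**

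Inputs: SAP section 1.2 gives Visit 5 as "Dispense Lens 2 [2 (at least 48 hours) - 4 days after the end of Visit 4", so the washout is 2 to 4 days. Each follow-up interval is 7 to 8 days, so each wear period is 14 to 16 days. The target is 92 completers.

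- Window = washout − 1 day = 2 − 1 to 4 − 1 = 1 to 3 days.
- Subject-days in the window: 92 × 1 = 92 to 92 × 3 = 276.
- Scheduled on-lens subject-days, both periods: 92 × 28 = 2,576 to 92 × 32 = 2,944.
- Share of the time from Visit 2 to Visit 7: lowest 1/(16 + 2 + 16) = 1/34 = 2.9%; highest 3/(14 + 4 + 14) = 3/32 = 9.4%.

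**What one event would change**

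Assume 92 subjects exposed to a lens and exact (Clopper-Pearson) 95% limits.

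- No tabulated event: 0/92, upper limit 1 − 0.025^(1/92) = 3.9%.
- One event: 1/92 = 1.1%, interval 0.03% to 5.9%.

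This contrast would arise only if the washout event were moved into the treatment-emergent numerator. There is a good reason not to do that. Visit 7 is the exit visit, so completers have no matching off-lens window after Period 2, and merging would add off-lens follow-up to Period 1 only. With a separate table instead, the treatment-emergent table still reads 0/92. The new table would show the event over subjects who wore that lens in Period 1. Under an assumed 1:1 allocation (the ratio is redacted) that is 92/2 = 46, and 1/46 = 2.2%. This restates one line of a listing.

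**The case for a change.** The strongest contrary case has four parts.

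- **The output count is right.** On the visible text, a device-related event with onset in this window is tabulated under neither lens. That stands as a description of the plan.
- **Serious and significant nonserious events.** Protocol section 12.6 says these will be identified, but the SAP's tables for them are treatment-emergent only. It is uncertain whether that protocol sentence reaches washout events. They are nevertheless listed.
- **Biomicroscopy.** Increases of two or more grades are counted within a period, and Visit 5 is the Period 2 baseline. A sign first seen at Visit 5 is therefore not counted as an increase on the Period 1 lens. That stands too, although its grade appears in the by-visit table.
- **Early stoppers.** The window of 1 to 3 days holds for completers. For a subject who stops the Period 1 lens early and never wears the second, the visible text does not say when the window closes. The documents give no count of such subjects. If an event is classed by its onset, which is my reading, an event that makes someone stop wear began on the lens and is already treatment-emergent.

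Taken together, these points show that one more descriptive table could be produced cheaply from data already collected. They do not show that an event is lost, that the two documents disagree, or that one lens is favoured. For a handful of events, a listing also carries more detail than a nearly empty incidence table.

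**Conclusion.** The concern does not hold. Listing washout events apart from treatment-emergent ones is a prespecified choice made in the protocol and carried through in the SAP. Followed as written, the plan reports every such event, and the lens worn before it can be identified. The rule is set by time and not by lens, so it creates no preference between products.

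The window is about 1 to 3 days for completers, 2.9% to 9.4% of the time from Visit 2 to Visit 7. Nothing in the documents shows that even one device-related event is expected in it. An extra table would leave every existing table and listing as it is. It would alter no conclusion in a study without safety hypotheses or success criteria. It is a matter of reporting preference.

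This rests on the visible text. Parts of both safety-set definitions (protocol section 12.2.1 and SAP section 2.1) and the title of SAP section 5.4 are redacted, and no text of section 5.4 is visible. A further attribution rule may stand there, which is another reason not to call this an omission.
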